OG-6219 and its primary metabolite FOR-1011 are both metabolized primarily by Cytochrome (CYP) CYP3A4. No reversible or time-dependent inhibition of any CYP enzymes was observed for either OG-6219 or FOR-1011 at relevant concentrations in vitro, but both compounds induce CYP3A4 in a concentration-dependent manner. Clinical drug interaction studies were not performed yet. Therefore, concomitant administration of moderate and strong CYP3A4 inhibitors and inducers and sensitive substrates of CYP3A4 will be prohibited. OG-6219 and FOR-1011 were found to inhibit P-glycoprotein (P-gp) and/or Breast Cancer Resistance Protein (BCRP) transporters in vitro, thus concomitant administration of OG-6219 with sensitive P-gp and BCRP substrates should be avoided (see [Appendix 7](#)). Concomitant medications that are sensitive substrates of P-gp or BCRP should be administered at least 4 hours apart from administration of OG-6219.

In both toxicology species (rat and cynomolgus monkeys), statistically significant increases in liver weights were observed in OG-6219 treated groups which may be attributed to CYP3A4 induction. Full recovery was observed. No effect on biomarkers of hepatic function, including liver enzymes, albumin, and bilirubin was observed and there were no microscopic changes in the liver. In Phase 1 in a total of 71 participants treated with OG-6219 for up to 14 days at doses up to 150 mg BID, no clinically relevant changes in indicators of liver function were observed. However, no clinical data on effects on liver function with longer exposure are available. To manage the risk of potential hepatotoxicity, participants with pre-existing clinically, or serologically identifiable liver disease will be excluded, and liver function will be monitored via laboratory assessments throughout the study in monthly intervals.

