[REDACTED] An increase in liver weight in both rats and cynomolgus monkeys likely attributable to CYP3A4 induction; however, no pre-clinical or Phase 1 data suggest any potential liver toxicity. In addition, no data on fertility and early embryonic development are available. CCI [REDACTED]
[REDACTED]
[REDACTED]

Therefore, in this current Phase 2a/b study, comprehensive panels assessing hematology, clinical chemistry, urinalysis parameters (CCI [REDACTED]), will be closely monitored. Refer to Section 8.4.6 for details of AESIs.

OG-6219 and its primary metabolite FOR-1011 are both metabolized mainly by CYP3A4 and were found to induce CYP3A4 in vitro. No clinical drug interaction studies were conducted to date. However, concomitant administration of OG-6219 with sensitive P-gp and BCRP substrates should be avoided (see Appendix 7).

To manage these risks, necessary precautions to prevent pregnancy will be taken in this study, including pregnancy tests prior to and during the study, and acceptable effective methods of contraception are required for participation. The effect of OG-6219 on systemic hormones, as well as general safety, including ECG and bone effects, will be closely monitored, including blood draws at different points during the first treatment cycle visit and each site visit at the start of next C treatment cycles, as well as during safety follow-up. Cycle length will be monitored by C self-reported bleeding pattern in an eDiary. The ECG measurements will be performed at relevant exposure time points, including T_{max} on Day 1 at the Randomization Visit and after achieving steady state (visit at CC [REDACTED] of the first menstrual cycle after randomization). CCI [REDACTED]
[REDACTED]

[REDACTED] Suicidality will be monitored throughout the study employing a validated questionnaire C-SSRS. Based on

determination of positive C-SSRS results for suicidality, the participants will be discontinued from the study medication and referred to a specialist at the Investigator's discretion for further evaluation. In addition, the positive results from C-SSRS evaluation will have to be treated as an SAE and reported to the Sponsor in a timely manner. Concomitant medications that are sensitive substrates, as well as moderate or strong inhibitors or inducers of CYP3A4 are prohibited. Concomitant medications that are sensitive substrates of P-gp or BCRP should be administered at least 4 hours apart from administration of OG-6219.

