6.8.2 Prohibited Medications and Other Products

The following concomitant medications, therapies, and products are prohibited during study participation (refer to [Table 2](#), [Appendix 6](#), and [Appendix 7](#)). Please note these additional clarifications for prohibited medications/products:

- Sensitive substrates, moderate, and strong inhibitors, or inducers of CYP3A4 ([Appendix 7](#)).
- Sensitive substrates of P-gp and BCRP
Note: For the P-gp and BCRP substrates: they should be administered at least 4 hours apart from OG-6219 ([Appendix 7](#)).
- Endometriosis treatments for symptom relief except rescue medication allowed by protocol ([Appendix 6](#)).
Note: Participants can NOT use local anesthetic (eg, lidocaine patches) NOR receive acupuncture while participating in the study
- The use of analgesic medication different than the rescue medication is prohibited (this is referred as prohibited pain medication, see [Appendix 8](#)).

CCI

- Surgical treatment of endometriosis and use of intrauterine devices are prohibited from start of the Screening Period until EOS.

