Appendix 7 Prohibited CYP3A4 Substrates, Inducers, and Inhibitors; and P-gp and BCRP Substrates

The following medications are prohibited at any time during this study.

Note: The list is intended to be a guidance and may not include all medications in the respective categories.

CYP3A4 Substrates (Sensitive)	Alfentanil, apixabane, alprazolam, aprepitant, atorvastatin, budesonide, buspirone, colchicine, conivaptan, cyclosporine, darifenacin, darunavir, dronedarone, ebastine, eletriptan, eliglustat, eplerenone, everolimus, felodipine, indinavir, lomitapide, lovastatin, lurasidone, maraviroc, midazolam, naloxegol, nisoldipine, pimozide, quinidine, quetiapine, rifabutin, rilpivirine, rivaroxaban, saquinavir, simvastatin, sirolimus, tacrolimus, ticagrelor, tipranavir, tolvaptan, triazolam, and voclosporine.
CYP3A4 Inducers (Moderate and Strong)	Amprenavir, armodafinil, avasimibe, bosentan, carbamazepine, echinacea, efavirenz, etravirine, modafinil, nafcillin, nevirapine, phenobarbital, phenytoin, primidone, rifampin, and rufinamide.
CYP3A4 Inhibitors (Moderate and Strong)	Amiodarone, amlodipine, atazanavir, boceprevir, bicalutamide, chlorzoxazone, cimetidine, cilostazol, ciprofloxacin, clarithromycin, clotrimazole, cobicistat, cyclosporine, danoprevir, diltiazem, erythromycin, fluconazole, fluvoxamine, fosamprenavir, fluoxetine, ginkgo, goldenseal, grapefruit juice, isoniazid, istradefylline, itraconazole, ivacaftor, ketoconazole, lopinavir, mibefradil, nefazodone, nelfinavir, nicardipine, paritaprevir, posaconazole, products containing Seville oranges, ranitidine, ranolazine, rifabutin, ritonavir, telaprevir, telithromycin, tiranavir, tofisopam, troleandomycin, verapamil, voriconazole, and zileuton.
Sensitive substrates for P-Glycoprotein (P-gp)	Digoxin, dabigatran etexilate, edoxaban, fexofenadine, loperamide, morphine Note: should be administered at least 4 hours apart from OG-6219
Sensitive substrates for Breast Cancer Resistance Protein (BCRP)	Rosuvastatin, sulfasalazine, methotrexate, prazosin, glyburide, teriflunomide, cladribine Note: should be administered at least 4 hours apart from OG-6219

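### P-gp and BCRP substrates are listed as prohibited in Appendix 7 and Section 6.8.2, yet the same places tell sites to give them at least 4 hours apart from OG-6219

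*Protocol*

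**What the plan says.** Appendix 7 of the protocol has five rows: CYP3A4 sensitive substrates, CYP3A4 inducers, CYP3A4 inhibitors, sensitive P-gp substrates and sensitive BCRP substrates. Its lead-in is "The following medications are prohibited at any time during this study". The last two rows each carry "Note: should be administered at least 4 hours apart from OG-6219".

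Section 6.8.2 introduces its list with "The following concomitant medications, therapies, and products are prohibited during study participation". Sensitive P-gp and BCRP substrates are one of the bullets, and beneath that bullet stands "Note: For the P-gp and BCRP substrates: they should be administered at least 4 hours apart from OG-6219".

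Section 2.3.1 says "concomitant administration of OG-6219 with sensitive P-gp and BCRP substrates should be avoided" and, shortly after, also gives the 4-hour instruction. Section 2.3.3 carries both statements too, the second as "Concomitant medications that are sensitive substrates of P-gp or BCRP should be administered at least 4 hours apart from administration of OG-6219". Where Section 2.3.3 speaks of a ban, it names only the CYP3A4 classes: sensitive substrates, "as well as moderate or strong inhibitors or inducers of CYP3A4 are prohibited".

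On eligibility (Section 5.2), criterion 25 excludes use of treatments that could interfere with the study or its interpretation, and cites Appendix 7 as a whole. Criterion 26 also cites Appendix 7, but it and its washout of 30 days or 10 half-lives are worded around CYP3A4.

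**The concern.** A drug that is banned throughout the study has no permitted dosing interval, so the lead-ins and the notes cannot both be literally true. A site that follows the lead-in would exclude a user of these drugs or record a deviation. A site that follows the note would enrol and dose her, with the two drugs separated in time.

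The protocol attaches consequences to the difference. Sections 5.0 and 8.0 rule out waivers. Section 7.1 requires a participant enrolled against the criteria to stop study treatment, save for rare exceptions. Section 7.2 lists erroneous inclusion, and inability to comply with the rules on prohibited medication, among the reasons for discontinuation. Deviations are tabulated for the FAS (Protocol 9.4.8.1, SAP 8.2.2), so the reported counts would depend in part on which sentence a site followed.

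There is a safety side as well. Section 2.3.1 reports transporter inhibition in vitro and says that clinical interaction studies had not yet been done, and the drugs named include digoxin, dabigatran, edoxaban and methotrexate. An ambiguous rule for such drugs should not be left to each site.

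**Working it through.** No figure in the plan bears on this point, so the check is a comparison of the current text plus one count.

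| Place in the protocol | CYP3A4 classes | P-gp and BCRP substrates |
|---|---|---|
| 2.3.1 | prohibited | avoid co-administration; 4 hours apart |
| 2.3.3 | prohibited | avoid co-administration; 4 hours apart |
| 5.2, criterion 25 | within Appendix 7 | within Appendix 7, no limit to CYP3A4 |
| 5.2, criterion 26 | excluded, washout stated | not plainly covered, no washout stated |
| 6.8.2 | prohibited | prohibited; note: 4 hours apart |
| Appendix 7 | prohibited at any time | prohibited at any time; note: 4 hours apart |

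1. The CYP3A4 column is consistent throughout. The other column is not, and two of its cells (6.8.2 and Appendix 7) contradict themselves.

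2. The two risk sections can be read as one instruction, namely not to take the drugs together but to separate them. They do not call these drugs prohibited. The two operative lists do.

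3. Eligibility turns on criterion 25. If Appendix 7 is a ban on all five rows, criterion 25 can be read to exclude users of P-gp and BCRP substrates. If the note is an exception, it need not. Criterion 26 does not settle this: read plainly it concerns CYP3A4, and no washout is given for the transporter substrates.

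4. Extent of the list. P-gp row: digoxin, dabigatran etexilate, edoxaban, fexofenadine, loperamide, morphine = 6. BCRP row: rosuvastatin, sulfasalazine, methotrexate, prazosin, glyburide, teriflunomide, cladribine = 7. Total 6 + 7 = 13. Appendix 7 describes its list as guidance that may be incomplete, so the classes are wider than the 13 names.

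5. Morphine carries the 4-hour note in Appendix 7. It is also an opioid, which Table 2 restricts, and it is named in Appendix 8. A site reading only the Appendix 7 row would not be directed to the opioid restriction.

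6. Reach into the analysis. The MFAS (SAP 6.4) requires one dose and one later diary entry for DYS or NMPP; it does not exclude on concomitant medication. The Per-Protocol set (SAP 6.5) removes a participant for a deviation only when the deviation is graded critical or major and also has a major impact on the primary endpoint. Neither document gives the number of women taking these drugs, so no count of affected participants can be derived.

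**The case against.** The strongest reply is that the notes are meant as an exception and most readers would take them so. Section 6.8.2 presents its bullets as clarifications, the 4-hour note sits directly under the P-gp and BCRP bullet, Sections 2.3.1 and 2.3.3 reserve the word prohibited for the CYP3A4 classes, and the absence of a washout fits a class that is not exclusionary. On that view the lead-in is simply too broad for two of five rows. This is a plausible reading and may be what was intended. But no sentence says that the note overrides the ban, and criterion 25 still points to the whole appendix.

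Three further objections limit the consequences, and they stand.

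- Criterion 25 is qualified by possible interference with the study, so exclusion of every user is one reading and not a certainty.
- The stated mechanism is that OG-6219 and FOR-1011 inhibit the transporters. That bears on exposure to the other drug, and the documents give no route to a major effect on the pelvic pain score.
- Deviations are graded under a separate Protocol Deviation Management Plan (SAP 8.2.2), and set membership is agreed before database lock (SAP 6.1). That plan is not among the documents, and it may already deal with the matter.

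On timing, Amendment 06 projected that all participants would be randomized by the former interim timepoint, and the SAP is dated June 2025. A change of wording may come too late to affect screening. The classing of recorded use matters until the analysis sets are settled.

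**Conclusion.** The inconsistency is real and stands in current operative text, in Appendix 7 and Section 6.8.2, with Section 5.2 leaving the eligibility consequence open. It covers 13 named drugs. Sites could differ on eligibility, on deviation status and on whether treatment must stop. The point is worth correcting because the rule concerns safety and eligibility and the correction is cheap.

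A reader might infer three stronger things that the documents do not support.

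- That eligibility reverses outright for every user. It rests on criterion 25 alone, and that criterion is qualified.
- That Per-Protocol membership follows each site's reading. SAP 6.5 also demands major impact on the primary endpoint, and membership is agreed centrally, so an effect is possible but probably small. The Per-Protocol analysis is a sensitivity analysis (SAP 8.3.6), and the primary MFAS analysis is not affected.
- That morphine is permitted under one reading and banned under the other. Table 2 restricts opioids either way, so what is missing is a cross-reference. Some of the surrounding analgesic text is redacted, so the full opioid rule cannot be judged here.

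The conclusion assumes that no site instruction outside the two documents has already settled the rule. The number of users is unknown, and no size in participants can be given.

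**What to change.** Reconcile Protocol Sections 2.3.1, 2.3.3, 5.2 (criteria 25 and 26), 6.8.2 and Appendix 7 to a single rule for sensitive P-gp and BCRP substrates. Which rule applies is for the sponsor to decide. The lead-ins of Appendix 7 and Section 6.8.2 should then match that rule for these rows. If the transporter substrates are meant to be treated differently from the CYP3A4 classes, they should stand apart from the table headed as prohibited. Criteria 25 and 26 should say whether they reach these drugs. The morphine entry should refer to the opioid restriction in Table 2.

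Before database lock, confirm that the Protocol Deviation Management Plan classes recorded use of these drugs in the same way across sites, including whether such use can count towards Per-Protocol exclusion.

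The cost is wording in one amendment or clarification letter and, if the plan is silent, one added line. No analysis, sample size or data collection changes.

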Appendix 8 Concomitant Pain Relief Medication

CCI

Nonsteroidal anti-inflammatory drugs (NSAID) and Others

Acetaminophen (Actamin, Altenol, Aminofen, Feverall, Genapap, Ofirmev, Tylenol)
Aspirin (also known as acetylsalicylic acid) (Ecotrin)
Celecoxib (CeleBREX, Elyxyb)
Diclofenac (Cataflam, Cambia, Dyloject, Lofena, Pennsaid, Rexaphenac, Solaraze, Voltaren, Voltaren-XR, Zipsor, Zorvolex)
Diflunisal (Dolobid)
Etodolac (Lodine, Lodine XL)
Fenoprofen (Expron, Fenortho, Nalfon, Profeno)
Flurbiprofen (Ansaid)
Ibuprofen (Actiprofen, Addaprin, Advil, Advil Liqui-Gels, Advil Migraine, A-G Profen, Bufen, Caldolor, Genpril, Haltran, Ibu, IBU 220, Ibu-8, Ibu-6, Ibu-4, Ibu-Tab, Midol IB, Motrin, Motrin IB, NeoProfen, Nuprin, Propinal, Q-Profen)
Indomethacin (Indocin, Indocin SR, Tivorbex)
Ketoprofen (Orudis, Orudis KT, Oruvail) / Dexketoprofen (Algoflex Neo, Keral)
Ketorolac (Sprix, Toradol)
Magnesium salicylate (Doan's Extra Strength, Doan's Regular, Keygesic-10, MST 600, Momentum, Novasal)
Meclofenamate (Meclomen)
Mefenamic acid (Ponstel)
Meloxicam (Anjeso, Mobic, Qmiiz, Vivlodex)
Nabumetone (Relafen, Refalen DS)
Nepafenac (Ilevro, Nevanac)
Naproxen (Aleve, Napronex, Flanax, mediproxen)
Oxaprozin (Daypro)
Piroxicam (Feldene)
Salsalate (Amigesic, Disalcid, Salflex, Salsitab, Mono-Gesic)
Sulindac (Clinoril)
Tolmetin (Tolectin DS, Tolectin 600)

Opioids

Hydrocodone: Vantrela, Hysingla ER, Zohydro ER
Hydromorphone: Exalgo(R), Palladone (R)
Meperidine: Demerol
Morphine: Avinza, Kadian, Arymo, MS Contin
Oxycodone: OxyContin, Roxicodone, Xtampza (TM)

Tramadol: Ultram

Combinations

Acetaminophen/aspirin, caffeine (Excedrin, Vanquish)
Acetaminophen / butalbital / caffeine / codeine (Fioricet with Codeine, Phrenilin with Caffeine and Codeine)
Acetaminophen / caffeine / dihydrocodeine (Dvorah, Panlor, Panlor DC, Panlor SS, Trezix, Zerlor)
Acetaminophen / codeine (Capital w/Codeine, Cocet , Codrix, Tylenol with Codeine, Tylenol #3)
Acetaminophen / hydrocodone (Anexsia, Co-Gesic, Hycet, Lorcet 10/650, Liquicet, Lorcet Plus, Lortab, Maxidone, Norco, Stagesic, Theracodophen Low 90, Verdrocet, Vicodin, Vicodin ES, Vicodin HP, Xodol, Zamiset, Zolvit, Zydone)
Acetaminophen / oxycodone (Endocet, Magnacet, Nalocet, Narvox, Percocet, Perloxx, Primlev, Prolate, Roxicet, Roxilox, Tylox, Xartemis XR, Xolox)
Acetaminophen/pentazocine (Talacen)
Acetaminophen/propoxyphene (Balacet, Darvocet A500, Darvocet-N 50)
Acetaminophen / tramadol (Tramapap, Ultracet)
Acetylsalicylic acid, sodium bicarbonate, and anhydrous citric acid (Alka Seltzer)
Aspirin / butalbital / caffeine / codeine (Ascomp with Codeine, Fiorinal with Codeine)
Aspirin/caffeine (Anacin, Bayer Aspirin, BC Arthritis, Goody's)
Aspirin / caffeine / dihydrocodeine (Synalgos-DC)
Aspirin / oxycodone (Endodan, Percodan)
Belladonna / opium (B&O Suppettes)
Buprenorphine / naloxone (Bunavail, Cassipa, Suboxone, Zubsolv)
Celecoxib / tramadol (Seglensis)
Diclofenac / misoprostol (Arthrotec)
Esomeprazole / naproxen (Vimovo)
Famotidine / ibuprofen (Duexis)
Hydrocodone / ibuprofen (Ibudone, Reprexain, Vicoprofen)
Ibuprofen/Caffeine (Algoflex duo)
Ibuprofen / oxycodone (Combunox)
Metamizole/ caffeine / drotaverin-hydrochloride (Quarelin)
Morphine / naltrexone (Embeda)
lansoprazole/naproxen (Prevacid NapraPAC)
Naloxone / pentazocine (Talwin Nx)
Naloxone / oxycodone (Targiniq ER)
Naltrexone / oxycodone (Troxyca ER)

Appendix 9 Country-specific Requirements

9.1 Specific requirements for France

Requirements for Section [8.1.5](#)

Race will not be collected for participants in France (see section [8.1.5](#)) as the collection and processing of personal data that reveals, directly or indirectly, the racial and ethnic origins, the political, philosophical, religious opinions or trade union affiliation of persons, or which concerns their health or sexual life, is prohibited. This is based on France's Data Protection Act No. 78-17 created the French Data Protection Authority (Commission Nationale Informatique et Libertés [CNIL]) (see [8.1.5](#)).

Appendix 10 Protocol Amendment History

The Protocol Amendment Summary of Changes Table for the current amendment is located directly before the table of contents (TOC).

Amendment 01 (16-Sep-22)

Overall Rationale for the Amendment:

Initial findings from non-clinical study have indicated that concomitant medications that are sensitive substrates of P-glycoprotein (P-gp) or Breast Cancer Resistance Protein (BCRP) should be administered 4 hours apart from OG-6219 intake. Therefore, the protocol OG6219-P001 has been amended to add this non-clinical information, address United States Food and Drug Administration (FDA) comments and to improve the readability.

Section number and Change	Description of Change (the information added is shown in quotes, and deleted information is shown as a strike-out)	Brief Rationale
Title page Synopsis	
 Protocol number updated to OG6219-P001-02 EU CTR number added 	To update administrative information.
Synopsis/ Rationale Section 4.2 (Scientific Rationale for Study Design) Throughout the document	
 The overall pelvic pain (OPP) denotes “endometriosis-related” overall pelvic pain, The non-menstrual pelvic pain score (NMPP) includes “pain associated with micturition, defecation, ovulation, intercourse” 	To provide clarity on pelvic pain (OPP and NMPP) definitions and their relationship only with endometriosis.
Synopsis/ Secondary Objectives and Endpoints Section 3 (Objectives and Endpoints)	
 For secondary objective #6, the corresponding endpoint sampling time for PK parameters C_{max}, T_{max}, and AUC_{tau} was clarified to be CCI 	To provide clarity on when PK assessment is to be performed.
Synopsis/ Secondary Objectives and Endpoints Section 3 (Objectives and Endpoints)	
 For the secondary objective #12 endpoint of mean change from BC to TRC3 “of the monthly dyspareunia score” was added 	To provide clarity that from BC to TRC3 relates to the monthly dyspareunia score.
Synopsis/Statistical Methods Section 9.5 (Interim Analysis)	
 IA was added to the synopsis Interim psychometric evaluation of blinded data was added during IA 	To include psychometric analysis of blinded data in the IA.
Section 1.3 (Schedule of Activities)	
 In footnote e: clarified that the PAP smear should be performed “at Screening” 	To provide clarity on when PAP smears are to be performed.

Section number and Change	Description of Change (the information added is shown in quotes, and deleted information is shown as a strike-out)	Brief Rationale
Section 1.3 (Schedule of Activities) CCI [REDACTED]	
 CCI [REDACTED] Additional changes were made to the section title and CCI [REDACTED] to be entered in the eCRF 	To provide clarity on CCI [REDACTED]
Section 2.3.1 (Risk Assessment) Section 2.3.3 (Overall Benefit Risk Conclusion) Section 5.3 (Lifestyle Considerations) Appendix 5 (Contraceptive and Barrier Guidance and Collection of Pregnancy Information)	
 Clarified acceptable contraceptive use Added that participants who are willing to reliably use “an acceptable effective method for contraception” may be eligible. The acceptable methods include effective methods of contraception (references to double barriers and highly effective contraception were removed) 	To clarify acceptable methods for contraception, use and correct the contraceptive terminology related to effective versus highly effective methods based on CTFG guidance ⁶⁵
Section 2.3.1 (Risk Assessment) Section 2.3.3 (Overall Benefit Risk Conclusion) Section 6.8.2 (Prohibited Medications and Other Products) Appendix 7	
 Added “OG-6219 and FOR-1011 were found to inhibit P-glycoprotein (P-gp) and/or Breast Cancer Resistance Protein (BCRP) transporters in vitro, thus concomitant administration of OG-6219 with sensitive P-gp and BCRP substrates should be avoided.” Concomitant medications that are sensitive substrates of P-gp or BCRP should be administered at least 4 hours apart from administration of OG-6219. The lists of medications that are sensitive substrates for P-gp and BCRP were added to Appendix 7. 	To specify how medications that are sensitive substrates of P-gp or BCRP should be administered in relation to OG-6219 intake to avoid possible DDIs with regard to these transporters.
Section 1.3 (SOA) – footnote y Section 2.3.1 (Risk Assessment) Section 2.3.3 (Overall Benefit Risk Conclusion) Section 7.2 (Participant Discontinuation/Withdrawal from the Study) Section 8.3.4 (Columbia-Suicide Severity Rating Scale (C-SSRS))	
 Added “Based on determination of positive C-SSRS results for suicidality and its severity, the participants will be discontinued from the study medication and referred to a specialist at the Investigator’s discretion for further evaluation. In addition, the positive results from C-SSRS evaluation will have to be treated as an SAE and reported to the Sponsor in a timely manner.” Added the study discontinuation criterion for “participants who experience suicidal ideation or attempt suicide” Added the following sentence: “Suicidality will be monitored throughout the study employing a validated questionnaire C-SSRS.” 	To provide steps taken with a positive C-SSRS result.

Section number and Change	Description of Change (the information added is shown in quotes, and deleted information is shown as a strike-out)	Brief Rationale
Section 5.1 (Inclusion Criteria) Table 2: Prohibited Medication and Other Substances Section 8.2.2.4 Prohibited Pain Medication Use	
 Clarified that CCI (ie, CCI of other NSAID or non-opioid pain medications for acute conditions other than ERP is permitted 	For clarification CCI of pain medication in Inclusion Criterion #13 and other sections in the protocol as listed.
Section 5.2 (Exclusion Criteria)	CCI	For clarification.
Section 5.2 (Exclusion Criteria)	
 Corrected EC#3 to include “clinically” as follows: Has a “clinically” significant gynecologic condition Revised exclusion criteria #14 as follows: Has a known human immunodeficiency virus infection, “and/or” active, recurrent, or chronic infection (eg, hepatitis A, B, or C virus) 	For clarification.
Section 6.6 (Continued Access to Study Treatment after the End of the Study)	
 Changed as follows: The Sponsor will not provide additional care to the participants after they leave “complete or discontinue” the study. 	To use consistent terminology.
Section 6.9 (Study Treatment Accountability)	
 Corrected that the quantity of dispensed study treatment will be recorded on study treatment accountability forms and entered in the “IRT”. Corrected that the use of rescue medication will also be recorded in the IRT “and eDiary” 	To correct of documentation methods used.
CCI		To correct the error.
Section 8.3.2 (Vital Signs)	
 Deleted specific instructions related to blood pressure 	Standard procedure.
Section 8.4.1 (Time Period and Frequency for Collecting AE and SAE Information) – Table 7	
 Revised that for Overdose, report if receiving CCI or other CCI medication “(including Rescue Medication)” Added, “For SAEs, standard procedures for reporting (within 24 hours) must be followed” 	To clarify the use of Rescue Medication and to specify that for SAE the standard procedures for reporting (within 24 hours) must be followed.

Section number and Change	Description of Change (the information added is shown in quotes, and deleted information is shown as a strike-out)	Brief Rationale
Appendix 2 (Regulatory, Ethical, and Study Oversight Considerations)	
 For Quality Assurance, added that the “eDiary” data will be transmitted to the Sponsor or designee electronically. 	For clarification.
Appendix 3 (Clinical Laboratory Tests)	
 In Table 9 (Protocol-required Safety Laboratory Tests) the following coagulation tests were added: prothrombin time, activated partial thromboplastin time, and antithrombin III Revised Urinalysis as follows: Microscopy (if clinically indicated) 	Added evaluations for coagulation as recommended by the FDA, and indicated that Microscopic evaluation for Urinalysis will be for all participants.
Appendix 7	
 Added, “Note: The list is intended to be a guidance and may not include all medications in the respective categories” 	Added guidance.
Appendix 9 (Protocol Amendment History)	
 Section added 	Section to be added for amendments.
Throughout the document	
 Minor editorial updates 	For better readability.

Amendment 02 (03-Jan-2023)

Overall Rationale for the Amendment:

The protocol OG6219-P001-01 was amended to address European Medicines Agency (EMA) feedbacks.

Section number and Change	Description of Change (the information added is shown in bold, and deleted information is shown as a strike-out)	Brief Rationale
Section 1.3 Serum Pregnancy Test (β -hCG)	
 Serum Pregnancy Test was added to CCI 	Agreement with EMA suggestion
Section 1.3 Footnote g	
The footnote g was changed to:
 
The UPT is centrally provided. If any menstrual cycle delay is noted, the participant must immediately perform UPT and contact clinic to schedule a visit as soon as possible and the Sponsor must be contacted. Additional UPT can be dispensed as needed.
	Clarify that when a menstrual delay is noted, the participant must immediately perform UPT and contact the clinic.
Introduction	
 The introduction was modified as follows: The HSD17β1 in primates, is primarily expressed in the placenta and ovary and to a lesser extent in the endometrium, adipose tissue, and prostate. The HSD17β 	Include recent published information

Section number and Change	Description of Change (the information added is shown in bold, and deleted information is shown as a strike-out)	Brief Rationale
	
expression in the human endometrium is not detected until Day 14 of the menstrual cycle
 
HSD17β1 expression is seen in the eutopic endometrium throughout the cycle. The HSD17β1 and HSD17β2 are both expressed in endometrium and endometriotic implants; however, there is an imbalance between HSD17β1 and β2 in endometriotic lesions as compared to normal endometrium (eutopic endometrium).
 
 In a recently published study, in which protein levels of different enzymes were determined in both eutopic endometrium and endometriotic lesions, eutopic endometrium presented higher levels of aromatase, compared to steroid sulfatase (STS) or HSD17β1, while endometriotic lesions had superior levels of STS and HSD17β1. 	
2.3.1 Risk assessment	
 Modified the following: Any potentially deleterious effect on the endometrium will be monitored by TVUS or transabdominal (pelvic) ultrasound and endometrial biopsies during Screening up to TRC3 CCI [REDACTED] 	Clarification
2.3.1 Risk assessment	
 Modified the following: However, as the effect of OG-6219 on fertility and early embryonic development and pre-and post-natal development has not been studied at this time, the risk of reproductive toxicity cannot be considered fully characterized. 	Clarification
2.3.3 Overall Benefit Risk Conclusion	
 Clarified that the lower doses of CCI [REDACTED] BID are planned based on Phase 1 PK modeling data 	Agreement with EMA suggestion
4.3 Justification for dose	
 Modified the following: In this Phase 2a/b study, the lower doses of CCI [REDACTED] BID planned-are based on Phase 1 PK modeling data. In this Phase 2a/b study, all the lowest dose of CCI [REDACTED] BID planned is expected to be less effective or have no effect, assuming dose linearity and observed plasma PK. 	All three dose levels chosen (CCI [REDACTED] BID) are anticipated to be efficacious based on Phase 1 PK modeling data (therefore 'no effect' is incorrect).

Section number and Change	Description of Change (the information added is shown in bold, and deleted information is shown as a strike-out)	Brief Rationale
5.1 Inclusion Criteria Inclusion criterion 04 (IC04)	
 IC04 was modified as follows: Has had spontaneous (ie, without hormonal therapy), regular, menstrual cycles with a cycle length between 21 to 32 days (inclusive) for the past 2 1 months before V1. Note: Peri-menopausal women have irregular menstrual cycles, and don't meet this inclusion criterion, and should not be included. 	Clarify the peri-menopausal participants are excluded
5.2 Exclusion Criteria Exclusion criterion 7 (EC7)	
 EC7 was modified as follows: Has no documented normal Papanicolaou (PAP) test within the timeline of current standard of care guidelines or has a significantly abnormal PAP test at Screening (V1) (ie, atypical squamous cells, low grade squamous intraepithelial lesion, high grade squamous intraepithelial lesion, atypical glandular cells [any type], squamous cell carcinoma, or adenocarcinoma [in situ or invasive]). The presence of high-risk human papillomavirus (HPV), regardless of PAP result, is exclusionary (e.g. atypical squamous cells). 	Clarification
5.2 Exclusion Criteria Exclusion criterion 14 (EC14)	
 EC14 was modified as follows: Has a known human immunodeficiency virus infection, and/or an acute or active, recurrent/relapsing, or chronic infection (eg, hepatitis A, B, or C virus). 	Clarification
5.2 Exclusion Criteria Exclusion criterion 22 (EC22)	
 EC22 was modified as follows: Based on the known metabolism of OG-6219 there are no effects of alcohol, caffeine, or tobacco associated with study treatment. However, during the study participants are asked to refrain from 
 Excessive tobacco use and smoking CCI CCI based on Investigator's discretion. 	Clarified CCI CCI is an exclusion criterion
5.2 Exclusion Criteria Table 2	
 Table heading changed to: Prohibited Medication, Contraceptive Devices and Other Substances Also Modified the text in the table as follows: 
 The following medications, contraceptive devices and other substances are prohibited at any time 	Clarify that Contraceptive Devices are also listed in the table as being prohibited

Section number and Change	Description of Change (the information added is shown in bold, and deleted information is shown as a strike-out)	Brief Rationale
	during the participant's participation in this study	
	
 Section subheading changed to: Prohibited Medications: Hormones and Contraceptive Devices 	Clarify that Contraceptive Devices are listed in the table as being prohibited
	
 Included Hormonal Replacement Therapy (HRT) 	Specify that HRT is a prohibited medication
	
 Changed the description for CCI [REDACTED] Footnote b was modified as follows: Participants with an No intrauterine device IUD (non-hormonal) must be removed before on the day of the Screening Visit are excluded. 	Clarify that any CCI taken for chronic pain is prohibited
5.3 Lifestyle consideration	
 The following changes were made: Excessive tobacco uses and smoking has been restricted based on Investigator's discretion. Abuse of alcohol is prohibited. Alcohol intake should be limited to 2 to 3 units per day, not to exceed 14 units per week. Active use of illicit drugs CCI is prohibited. Note: CCI (prescribed) for chronic pain use is prohibited. Refer to Table 2 for a list of prohibited medications. 	Clarification on use of CCI
8.1.5 Demography	
 Specific requirements were added for France 	Specify requirements for France on collection of demography data
8.3.6 Endometrial Biopsy	
 The following changes were made: If the results of an endometrial biopsy are abnormal the participant will be informed of the results and appropriate clinical follow-up is required. If abnormal results are at Screening, the participant will be screen failed. If the results of an endometrial biopsy are abnormal the participant will be informed of the results and advised as to any medically appropriate follow up. 	Clarification on endometrial biopsy results

Section number and Change	Description of Change (the information added is shown in bold, and deleted information is shown as a strike-out)	Brief Rationale
8.4.4 Regulatory Reporting Requirements	
 The following was added: SUSAR reports will be submitted electronically (gateway to gateway) from the sponsor's safety database to the EudraVigilance Clinical Trial Module, in accordance with the EU Clinical Trial Regulation. 	Added procedure for reporting of SUSARs by the sponsor
Appendix 2	
 Recruitment information was added and the heading was changed to Recruitment and Informed Consent Subheading styles were changed For Data Protection, the following was added: The contract between sponsor and study sites and any applicable third part involved in the trial specifies responsibilities of the parties related to data protection, , including handling of data security breaches and respective communication and cooperation of the parties. 	Include recruitment procedures. Subheading styles were changed for easier viewing and navigation.
Appendix 5	
 The following was added: Dual non-hormonal contraception method 
 Male condom combined with any one of the following barrier methods: 
 With spermicide Diaphragm with or without spermicide Cervical cap with or without spermicide Vaginal sponge impregnated with spermicide 
Note:
 
 Male and female condom should not be used at the same time If permitted by local guidelines, contraceptive gels with other barrier methods (eg. diaphragm or cervical cap) may be used in countries where spermicides are not available. 	Clarify contraceptive requirements.
Appendix 8	
 This is a new appendix that was added: Concomitant Pain Relief Medication CCI 	Clarify pain medications allowed CCI

Section number and Change	Description of Change (the information added is shown in bold, and deleted information is shown as a strike-out)	Brief Rationale
Appendix 9	
 Specific requirements for France were added as race will not be collected 	EMA feedback based on France's Data Protection Act No. 78-17 created the French Data Protection Authority (Commission Nationale Informatique et Libertés [CNIL])
Appendix 10	
 Protocol Amendment History was added 	Template specification
Appendix 11: Data Protection	
 The following was added The contract between sponsor and study sites specifies responsibilities of the parties related data protection, including handling of data security breaches and respective communication and cooperation of the parties. Information technology systems used to collect, process, and store study-related data are secured by technical and organizational security measures designed to protect such data against accidental or unlawful loss, alteration, or unauthorized disclosure or access. In the event of a data security breach, appropriate mitigation measures will be implemented. 	Clarify data protection procedures
Throughout the protocol	
 Minor edits and corrections 	Clarity

Amendment 03 (10-Feb-2023)

Overall Rationale for the Amendment:

The protocol OG6219-P001-01 has been amended to address Food and Drug Administration (FDA) questions.

